#### 6.3 Participant recruitment

Following ethical approval, patients will be approached by joint message on the LUPUS UK HealthUnlocked forum by LUPUS UK and research staff, with the study information detailed and the participant information sheet attached. A minimum of 24 hours will be left before the consent form and questionnaire are made available on the site. Consent will be returned with the questionnaire. We require 180 participants. If recruitment numbers are not satisfactory, prospective ppts will be approached through lupus UK support groups, other health forums and LUPUS UK Facebook page.

Phase 2 questionnaires and/or the online link will be sent to all LUPUS UK members by email and/or post with information sheets and made available online. The adapted versions for RA and fibromyalgia Ppts will be made available on the RA and fibromyalgia HealthUnlocked forum with an information sheet. Healthy friend controls will be recruited by Ppts with lupus/ related disease giving a friend the online link to their information sheet and questionnaire.

Physicians will be randomly selected, stratified by UK location. They will be approached by email, with contact details of the study team, a participant information sheet and online link to a questionnaire.

Purposive sampling will be used to select participants for interview from those who have given consent for this on their questionnaire response.

#### 6.4 Consent

The process for obtaining participant informed consent will be in accordance with ethical guidelines and Good Clinical Practice. Potential participants will be asked whether they wish to consider taking part, emphasising that participation is entirely voluntary. The participant information sheet, questionnaire and consent form will be made available online, on the forums and by post/email in phase 2. Participants may take as long as they wish to decide whether to participate in the study and will be given the opportunity to ask questions. Consent to be contacted to potentially participate in the interview study will be requested at the end of the questionnaires. Consent for the interview and to be audio-recorded will be verbally retaken at the start of the interview with the consent statements audio recorded.

#### 6.5 Participant withdrawal

Participants may be withdrawn from the email groups and/or the whole study either at their own request or at the discretion of the investigator. Participants will be made aware from the information sheet and in the allocation of group letter of how to withdraw and that it will not affect their medical care. Participants will be given the contact details of research staff and informed of how to report unacceptable or unkind emails within their groups in their group allocation letters. Participants who send unacceptable emails within their groups will be withdrawn from the group by study staff.

#### 6.6 Participant Follow Ups

Participants in phase 1 will be sent up to 3 reminders for non-response to the 4 and 12-month questionnaires. Physicians will be emailed up to two reminders for non-response to initial questionnaire request. If non-response, another random selection will be carried out from the same UK area.

#### 6.7 Analysis

Qualitative – Interviews and qualitative responses to the questionnaires will be coded and entered onto NVivo software with double coding to ensure reliability and repeatability. Analysis will be thematic. The consolidated criteria for reporting qualitative research (COREQ) will be followed.

Quantitative - SPSS will be used for entry and initial descriptive summary of quantitative data, stratified by characteristics and group. Data will also be presented graphically to ensure the results are easily accessible to patients, clinicians and policy makers.

Multiple regression analysis will be used to test variability between groups.

For phase 1, the primary outcome to be tested is mental wellbeing as measured by the validated Warwick Edinburgh Mental Wellbeing scale, between groups B to C, using the within-person change from baseline to month 4 and the primary endpoint (difference of differences), with illness outcome as a secondary outcome. Similarly, the comparison between groups A to C, and A to B will be examined as secondary tests, with a significance threshold of 5%/2 due to the reuse of groups. The primary hypothesis for phase 2 is illness impact. There will also be secondary tests for phase 1 and 2 using different endpoints such as 'the length of delay in diagnosis has a negative correlation with medication adherence'.

Following receipt of Group A's draft phase 2 questionnaires and suggested changes/additions, principal component analysis will be carried out to reduce questions and redesign the phase 2 questionnaire for distribution.

Correlations between two variables from groups and between the clinician/patient groups will be measured by Pearson correlation coefficient (if linearly related) or Spearman's correlation if not. Spearman's rank correlation will used for ordinal variables. Chi Squared testing will be used where appropriate.

Mixed methods analysis will be used at every stage. Validated tools for measuring QoL, Self-esteem, wellbeing and trust in physician will be used.

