## 4 Study Synopsis

Study title	The LISTEN study
	Listening: Involving SLE patients To Empower and Negotiate recognition
Short title	The LISTEN study
Chief Investigator	[name]
Chief Investigator's employing Institution	University of Cambridge
Funder	LUPUS UK
Study Duration	Phase 1 – small support email groups – duration 4 months, followed by questionnaire at 12 months after randomisation
	Phase 2A – Updated questionnaires to physicians, all LUPUS UK members, healthy control group and available online to RA and fibromyalgia patients. Response collection and analysis – 6 months
	Phase 2B – Interviews with physicians and patients – 6 months
	Total study duration (phases will overlap) – approx. 16 months
Participants	Phase 1 - Patients with SLE, UCTD, discoid/cutaneous lupus, Sjögren's syndrome or MCTD/Overlap disease responding to an invitation to complete online questionnaire introduced by online forums and support groups moderators.
	Phase 2A – All LUPUS UK members. RA questionnaire – ppts with self- verified RA. Fibromyalgia – ppts with self-verified fibromyalgia (available online on HealthUnlocked) Healthy friends – nominated friends of LUPUS UK members. Randomly selected physicians to receive physician questionnaire.
	Phase 2B – Purposively selected physicians and patients for interviews
Sample size	Phase 1 – Email support groups (180)
	60 in each of three groups
	Phase 2A – Questionnaire to all LUPUS UK members (5500), made available online on RA and fibromyalgia forums (expected 200 responses per disease category), link given by lupus forum members to healthy friends (expected 300 responses). Physician questionnaires (260)
	Phase 2B – Interviews until theoretical saturation reached. Estimated 15-25.
Objectives	1. To explore the acceptability and feasibility of peer support by small group email.
	2. To measure the impact of peer support and research involvement on the mental health, wellbeing, self-esteem and disease acceptance of patients with systemic autoimmune rheumatic diseases
	3. To empower patients and improve research quality and relevance by actively involving them in research into their own disease; generating

	research questions and research materials that are relevant to their priorities, needs and experiences.							
	4. To investigate key factors in effects of the disease and patient-physician interactions pre and post diagnosis on patient behaviour, mental health/ wellbeing and disease acceptance							

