	5. To compare lupus and related disease patients' wellbeing, mental health and perception of medical care with patients with RA, fibromyalgia and healthy friend controls							
Eligibility criteria	Participants aged 18 years or over							
	UK residents							
	• Participants with self- verified SLE, UCTD, discoid/cutaneous lupus, Sjögren's syndrome or MCTD/ Overlap disease.							
	• Phase 2 – Also includes Ppts with RA, fibromyalgia and healthy controls ('healthy controls' excluded if any significant chronic or acute severe illness)							
	• Physician questionnaires and interviews eligibility: A consultant or GP currently practising in the UK							
Description of intervention	
 
Phase 1 questionnaire will be made available through the online platform Qualtrics on LUPUS UK forum, lupus UK sufferers Facebook page and other online health forums if recruitment insufficient. This questionnaire contains questions on the impact of the disease and support on their wellbeing and mental health.
 
							
	2. Questionnaire respondents will be randomly allocated into one of 3 groups: Gps A and B will be divided into email support groups of 5-6 Ppts with the aim to provide peer support. In addition, Gp A will be given research tasks to discuss, including the pilot questionnaire to redesign in order to distribute to all LUPUS UK members. Gp C will be the control group.							
	3. The email support groups will communicate for 4 months, a which time all 3 Gps will receive another questionnaire to ascer any changes to their mental health, wellbeing, support perception and acceptance. They will also be asked to evaluate the posi and negative aspects of the group support. Another questionnaire will be sent 12 months after baseline questionnaire							
	4. The patient-adapted questionnaire will be made available online and by post to LUPUS UK members and online groups, including the RA and fibromyalgia forums and an adapted questionnaire link given to healthy friends by forum members. The physician questionnaire will be sent to a random sample of consultants and GPs. These questionnaires will contain questions on perceptions of support, wellbeing, mental health, medical relationships and patient behaviour.							
	
 
In-depth interviews will be carried out with purposively selected participants from questionnaire responses.
 
							
Analysis	Qualitative - Thematic analysis including using Nvivo software							

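### Arms A and B run in email groups of 5-6, but the named Phase 1 analysis has no email-group term, so its standard errors are too small if outcomes correlate within groups

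*Protocol*

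**What the plan says.** **Design.** The synopsis randomises individuals: "Questionnaire respondents will be randomly allocated into one of 3 groups". The size is "60 in each of three groups", and section 6.3 gives the total: "We require 180 participants". After allocation, "Gps A and B will be divided into email support groups of 5-6 Ppts with the aim to provide peer support". Arm A also receives research tasks to discuss. For the third arm the synopsis says only "Gp C will be the control group", with no email group described. On exposure: "The email support groups will communicate for 4 months", after which all three arms complete the follow-up questionnaire.

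**Analysis.** Section 6.7 makes B versus C the primary comparison, on within-person change in the Warwick Edinburgh scale from baseline to month 4. A-C and A-B are secondary, at 5%/2. The method sentence in the same section reads "Multiple regression analysis will be used to test variability between groups". The synopsis lists descriptive statistics, ANOVA, and correlations or regressions. The protocol does not mention email group as a factor, an ICC, a random effect or robust standard errors. The reference in section 6.7 to mixed methods means combining qualitative and quantitative work, not a mixed-effects model.

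**The concern.** The intervention is the exchange between members of a small group, so people in one group share their exposure for the whole period before the endpoint. A particularly supportive group, or one disturbed by an unkind member, can move several scores together. Sections 6.5 and 7.5 themselves foresee unacceptable behaviour within groups. Individual randomisation does not remove this correlation, because it arises afterwards.

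With groups in A and B and none in C, the design is partially nested. ANOVA and multiple regression in their ordinary form count 60 independent people in each arm. If outcomes correlate within groups, arms A and B carry less information than that. At stake are the width of the confidence intervals and the error rate of the primary test and both secondary tests. The point estimate is not biased by ignoring the grouping.

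**Working it through.** The protocol states no power, effect size, SD or ICC, so it has no figure of its own to reproduce beyond 3 × 60 = 180, which agrees with section 6.3.

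**Inputs from the protocol**
- n = 60 per arm (synopsis).
- Group size m = 5 or 6 (synopsis), so 60/5 = 12 or 60/6 = 10 groups in each of A and B.
- Level 2.5% for A-C and A-B (section 6.7).

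**Assumptions**
- ICC from 0 to 0.20; the protocol gives none.
- Two-sided 5% for B-C; this is implied, not printed.
- Everyone responds, and total variance is equal across arms.

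**Formulas**
- Design effect in a grouped arm: DE = 1 + (m − 1) × ICC. Effective size = 60/DE.
- B-C (and A-C), one arm grouped: true variance / assumed variance = (DE + 1)/2 = 1 + (m − 1) × ICC/2.
- A-B, both arms grouped: ratio = DE.
- Actual level = 2[1 − Φ(c/√ratio)], with c = 1.960 at 5% and c = 2.241 at 2.5%.

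**Worked case, m = 6, ICC 0.10**
- B-C: ratio = 1 + 5 × 0.10/2 = 1.25; √1.25 = 1.118; 1.960/1.118 = 1.753; actual level 8.0%.
- A-B: ratio = 1 + 5 × 0.10 = 1.50; √1.50 = 1.225; 2.241/1.225 = 1.830; actual level 6.7%.

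**Results (m = 5 / m = 6)**

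| ICC | True SE / assumed SE, B-C | B-C at nominal 5% | A-B at nominal 2.5% | Effective size of arm B |
|---|---|---|---|---|
| 0 | 1.00 / 1.00 | 5.0% / 5.0% | 2.5% / 2.5% | 60 / 60 |
| 0.01 | 1.01 / 1.01 | 5.2% / 5.3% | 2.8% / 2.9% | 58 / 57 |
| 0.02 | 1.02 / 1.02 | 5.5% / 5.6% | 3.1% / 3.3% | 56 / 55 |
| 0.05 | 1.05 / 1.06 | 6.2% / 6.5% | 4.1% / 4.5% | 50 / 48 |
| 0.10 | 1.10 / 1.12 | 7.4% / 8.0% | 5.8% / 6.7% | 43 / 40 |
| 0.20 | 1.18 / 1.22 | 9.8% / 11.0% | 9.5% / 11.3% | 33 / 30 |

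A-C has the B-C variance ratio but the 2.5% level. Its ratio at a given ICC equals the A-B ratio at half that ICC, so A-C runs at 4.1% / 4.5% at ICC 0.10 and 5.8% / 6.7% at 0.20.

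**Simulation check.** Fifty thousand trials per setting, with an ordinary t-test of B against C and equal total variance, gave 6.1% / 6.4% at ICC 0.05, 7.5% / 8.1% at 0.10 and 9.9% / 11.0% at 0.20. If the group effect instead adds to the variance of arm B, the highest figure was 11.7% (m = 6, ICC 0.20). A cluster-aware test (group means in B, individuals in C, Satterthwaite degrees of freedom) stayed at 4.9-5.2% throughout.

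**Fewer responders per group.** With 4 per group, the B-C ratio is 1 + 3 × ICC/2 = 1.075, 1.15 and 1.30 at ICC 0.05, 0.10 and 0.20. The actual levels are about 5.9%, 6.8% and 8.6%.

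**The case against.** The strongest reply is that the protocol leaves this open rather than getting it wrong. It never states independence. The regression sentence stands before the Phase 1 paragraph and may cover Phase 2 as well, and regression with cluster-robust errors is still regression. An analysis plan could add the group effect. It stands that independence is inferred from the usual form of the named methods. But these are the only between-arm methods named, and followed as written they ignore a grouping that the same document creates. An analysis plan that added a group term would be correcting this text.

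A second reply concerns the null. If the email groups affect nobody, and are formed without regard to prognosis, sharing a group creates no correlation and the ordinary test keeps its level. This also stands. Inflation needs groups that help in some cases and harm in others while averaging to zero. Confidence intervals, however, are too narrow whenever groups differ, whatever the average effect.

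Third, the protocol describes no facilitator per group, participants can report unkind emails, and senders are withdrawn (sections 6.5 and 7.5). This may lower the ICC. It does not make it zero, and it does nothing about groups that are unusually supportive.

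Fourth, withdrawal and non-response shrink the groups and with them the inflation, as the calculation for 4 responders shows. That is right, and the full-response figures should be read accordingly.

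**Conclusion.** The point holds in conditional form. For any positive within-group correlation, the named methods understate the standard errors of B-C, A-C and A-B. For the primary test the excess is slight at ICC 0.01-0.02, modest at 0.05, and roughly a doubling of the error rate only near 0.20. These figures rest on an assumed ICC range, full response and an implied 5% level. A-B is affected more, because both of its arms are grouped: at ICC 0.10 its actual level (5.8-6.7%) is above the 5% that the halved threshold was meant to divide.

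A reader might infer that the primary test does exceed 5%. The documents do not support that as a fact, since they give no ICC and at ICC 0 there is no excess. Nor does the full design effect apply to B-C, where only one arm is grouped.

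This should be fixed before analysis. It is not a flaw that invalidates the trial.

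**What to change.** State in section 6.7 that all Phase 1 between-arm comparisons account for email group in arms A and B, with each arm C participant as their own unit. A partially nested linear mixed model would do this, with a random email-group effect in A and B only and small-sample (Satterthwaite or Kenward-Roger) degrees of freedom. An equivalent cluster-aware method is equally acceptable, provided it allows for having only 10-12 groups per arm.

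Keep an email-group identifier in the analysis dataset. Section 7.3 describes questionnaire data entering SPSS identified only by participant ID, and nothing says that group membership goes with it. Report the estimated ICC, which also serves the feasibility objective.

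The change costs one sentence and one variable. The confidence intervals become somewhat wider: by the factors in the table, about 5-6% for B-C at ICC 0.05 and 10-12% at 0.10, before the small-sample degrees of freedom. As an illustration, for an assumed standardised difference of 0.5, power = Φ(0.5/√((DE + 1)/60) − 1.96). This is 78% at ICC 0, 74% / 73% at 0.05, 71% / 69% at 0.10 and 64% / 61% at 0.20 (m = 5 / m = 6). The loss comes from delivering the intervention in groups; the revised analysis only makes it visible.

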#### 7.2 Study Funding

The research costs for the study are funded by Lupus UK

#### 7.3 Records

Questionnaires will all be filled in electronically and will be captured on the Qualtrics online survey platform, under licence through the University of Cambridge. Data is transferred and held on the Qualtrics servers securely, within a specific location in the EU (https://www.qualtrics.com/privacy-statement/) Questionnaire data will be entered anonymously – identified only by the unique participant ID – into SPSS for data analysis.

Electronic data from Qualtrics and returned questionnaires by email will be transferred and stored on a Secure Data Hosting Service (SDHS) located on a firewall protected network (LAN), certified to ISO29001 security. At the close of the recruitment, all data study on the Qualtrics online will be deleted. Once uploaded to the SDHS, the questionnaire data will be accessible only by the research team using a two-factor authentication (password and security fob). Questionnaire data will be anonymised – identified by the participant ID – and transferred to SPSS for data analysis.

A document linking participant ID numbers and contact details will be stored on the SDHS, accessible only by the research team.

Anonymised data will be stored for five years post publication as required by APA Ethical Guidelines.

Each participant will be assigned a study identity code number for use on study documents and the database. All potentially identifying material will be removed. The investigator will make a separate confidential record on the secure data hosting service of the participants' names, addresses, contact details and identifying code to permit identification of all participants enrolled in the study. Study staff will adhere to GDPR 2018.

Interviews will be audio recorded and transcribed verbatim. All potentially identifying material will be removed from transcripts and Ppts will be assigned a number.

Study staff will adhere to the Data Protection Act 1998 and GDPR 2018.

#### 7.4 Insurance/Indemnity

The University of Cambridge as research sponsor indemnifies its staff, research participants and research protocols with public liability insurance and clinical trials insurance.

#### 7.5 Adverse Incident reporting

As this study is not a 'clinical trial of an investigational medicinal product (CTIMP)' it does not fall under The Medicines for Human Use (Clinical Trials) Regulations 2004 (as amended).

The research team will not collect data on adverse events (AEs), serious adverse events (SAEs) or suspected unexpected serious adverse reactions (SUSARs) as defined by these regulations. However, even in non-pharmaceutical research, such as this study, adverse incidents may still happen, for example;

- breach of confidentiality
- patient complains about any aspect of study

- deviation from study protocol (eg. recruiting before consent)
- equipment failure
- aggressive/ unacceptable behaviour of a participant towards the support group, researcher, staff or others.
- Responses highlights serious concern of risk to a patient

Concerns of risk to a participant will be immediately reported to the relevant authorities and the Chief Investigator. Unacceptable behaviour within support groups will result in expulsion of that participant from the group. Adverse incidents relating to the conduct of this research must be reported to the Chief Investigator within 5 working days of the researcher becoming aware of the incident

#### 7.6 Ethical approval

Ethical approval will be sought from the Cambridge Psychology Research Ethics Committee

#### 7.7 PPI Involvement

Individuals and focus groups of SLE/ related systemic autoimmune disease patients, approached through online forums and LUPUS UK support groups, have assisted with the development of the study.

Ongoing discussions with patients, LUPUS UK, rheumatologists and experts in the field will inform the further development of follow up studies. Five participants have been invited to represent patients' interest on this study. They have provided recommendations on the design of materials, such as information sheets and draft questions. They will review the final manuscript. LUPUS UK have been involved in the design of materials and will review the final manuscripts. Two consultant rheumatologists and two rheumatology registrars have been involved in the development of the study and review the manuscripts.

#### 7.8 Dissemination of research results

Results of the research will be published in peer-reviewed journals and findings presented to a wide audience. A lay summary will be provided for the LUPUS UK magazine

All participants in the study will have the option to request receipt of the final report.

#### 7.9 Proposed study timetable

	2019		2020				2021	
	Oct- Nov 2019	Dec 2019	Dec 19/J an 2020	Jan- Apr 2020	May 2020	May - Jul 2020	Aug- Dec 2020	Jan- Mar 2021
Produce draft protocol	Х							
Finalise participant information sheets and consent forms based on finalised protocol. Finalise pilot questionnaire	х							
Submit ethical proposal	Х							
Study introduced and questionnaire made available online			Х					
Patients randomly allocated to groups			Х					

4 months of Group communication		Х				
4 and 12 month Follow up questionnaire to all Ppts			Х		Jan X	
Patient-altered questionnaire to all LUPUS UK members, fibromyalgia and RA forum members and physicians			Х			
Data collection			Х	Х		
Interview s with patients and physicians				Х		
Analysis				Х	Х	
Write up					Х	Х
Dissemination/ Publication						Х

